5.3. Dexamethasone

5.3.1. Description

Corticosteroids, including dexamethasone, are a key component of SOC combination regimens in MM ([Burwick 2019](#)). Dexamethasone induces apoptosis and suppresses protein synthesis in MM cell lines in vitro ([Chauhan 2002](#); [Burwick 2017](#)). In clinical trials, dexamethasone has been shown to increase the activity of several classes of drugs, including alkylating agents, IMiDs, and PIs. In addition, dexamethasone is administered as premedication for monoclonal antibodies such as daratumumab and elotuzumab (Darzalex and Empliciti prescribing information).

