5.5. Required Premedication and Postmedication for SEA-BCMA

In Parts B through D, routine premedication for infusion reactions must be administered prior to SEA-BCMA infusion per the following regimen, unless contraindicated or recommended otherwise by the SMC or medical monitor:

- Antipyretic + Antihistamine: administer approximately 45 to 90 minutes prior to SEA-BCMA infusion (required for all subjects for all doses during Cycle 1 and Cycle 2)
 - Acetaminophen, oral, 650 to 1000 mg
 - Diphenhydramine, oral or IV, 25 to 50 mg (or equivalent H1 blocker)

If no IRR is experienced during Cycle 1 or Cycle 2: one or both premedications may be omitted starting with Cycle 3 Day 1 dose.

If IRR occurs despite acetaminophen + antihistamine, treat with supportive care based on symptoms.

For monotherapy subjects (not receiving dexamethasone), add:

- Methylprednisolone, IV, 100 mg (or equivalent dosage intermediate to long-acting corticosteroid) as required premedication 1 to 3 hours prior to next SEA-BCMA infusion. If this infusion is tolerated without IRR, methylprednisolone dose may be reduced to 60 mg (or equivalent dosage of intermediate to long-acting corticosteroid), administered either oral or IV, prior to subsequent doses.
- Additional premedications (eg, H2 blockers or leukotriene inhibitors) may be considered.

For combination subjects (receiving dexamethasone), add:

- H2 blocker (famotidine 40 mg IV or equivalent) as required premedication 45 to 90 minutes prior to all subsequent SEA-BCMA doses
- Additional premedications (eg, leukotriene inhibitors) may be considered.

For management of IRRs, including recommended concomitant therapy, see Section [5.7.1](#).

There are no required postmedications for SEA-BCMA.

For Parts C and D, refer to the dexamethasone package insert for detailed information on premedication and postmedication.

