	
 ○ Added exclusion criterion 18. Part C only: Any uncontrolled psychoses ● Discontinuation of study treatment ● Dose modifications ● Dexamethasone treatment 
 ○ Description, method of procurement, dose and administration, dose modifications, storage and handling, packaging and labeling, and preparation ● Required premedication and postmedication ● Study activities ● Response/Efficacy assessments ● Qualitative interviews ● Pharmacokinetic and immunogenicity assessments ● Determination of sample size ● Interim analyses ● Schedule of events ● PK, biomarker, and biomarker sampling time points 	
Section 1.1	
Updated with newly approved regimens for subjects with MM.
 
Removed the following sentence: SEA-BCMA in combination with an autologous T-cell product expressing an antibody-coupled T-cell receptor that recognizes antibodies, is currently being evaluated in a phase I study with MM subjects.
	Update with current information
Section 2, 9.2.6	Added exploratory endpoint to assess MRD in subjects with VGPR or better	To improve efficacy monitoring
Section 3.1.4	
Edited the following DLT:
 
 ● Any Grade ≥ 3 electrolyte asymptomatic laboratory abnormality that does not resolve, with or without intervention, to \leq Grade 1 or the baseline grade within 72 hours 	To improve safety monitoring
Section 3.1.7	Added section to allow treatment beyond progression under specified conditions.	To allow subjects receiving clinical benefit to be retreated
Section 3.3.1.1	Added rationale for selection of monotherapy expansion dose	Update with current information
Sections 5.2.3, 5.6.1	Updated dose modifications recommendations for SEA-BCMA monotherapy	To refine dose modification guidance; as IRRs have not yet been correlated with dose, and all IRRs that occurred during Cycle 1 Day 1 were successfully prevented by premedication at the next dose, dose reduction at the next dose can be considered but is not required

Section(s)	Change	Rationale
Section 7.7.3	Removed amylase and lipase from clinical laboratory tests	Streamline safety monitoring; no signal of pancreatic toxicity has been detected thus far on the phase 1 trial
Section 6.2, Appendix A, Appendix B	Removed q4wk SEA-BCMA dosing schedule	To remove unused dosing schedule

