2 STUDY OBJECTIVES AND CORRESPONDING ENDPOINTS

This study will evaluate the safety and antitumor activity of SEA-BCMA in patients with RRMM. Specific objectives and corresponding endpoints for the study are summarized below in **Error! Reference source not found..**

Table 1: Objectives and corresponding endpoints

Primary Objectives	Corresponding Primary Endpoint
Evaluate the safety and tolerability of SEA-BCMA monotherapy in subjects with relapsed or refractory multiple myeloma (RRMM)	Type, incidence, severity, seriousness, and relatedness of adverse events (AEs)
Identify the maximum tolerated dose (MTD) and/or optimal dose and schedule of SEA-BCMA monotherapy, and in combination with dexamethasone, in subjects with RRMM	Type, incidence, and severity of laboratory abnormalities Incidence of dose-limiting toxicities (DLTs)
Evaluate the safety and tolerability of SEA-BCMA in combination with SOC therapies in subjects with RRMM	
Secondary Objectives	Corresponding Secondary Endpoints
Identify a recommended single-agent dose and schedule of SEA-BCMA	Incidence of DLTs, cumulative safety and activity by dose level and schedule
Assess the pharmacokinetics (PKs) of SEA-BCMA	Maximum serum concentration and area under the serum concentration-time curve
Assess the immunogenicity of SEA-BCMA	Incidence of SEA-BCMA antitherapeutic antibodies (ATA)
Assess the antitumor activity of SEA-BCMA	Best response per the International Myeloma Working Group (IMWG) uniform response criteria (Kumar 2016) Objective response rate (ORR) Duration of objective response (OR) and complete response (CR) Progression-free survival (PFS) Overall survival (OS)
Exploratory Objectives	Corresponding Exploratory Endpoints
Study SGNBCMA-001 in document. 15-Aug-2023 SEA-BCMA	Statistical Analysis Plan Version Error! No text of specified style

Assess incidence and level of BCMA expression in RRMM and relationship to clinical response to SEA-BCMA	Characterization of BCMA expression on malignant plasma cells
Assess the pharmacodynamic effects and biomarkers of response, toxicity, and resistance to SEA-BCMA	Exploratory biomarkers of SEA-BCMA mediated pharmacodynamic effects
Assess minimal residual disease (MRD) in subjects with very good partial response (VGPR) or better	Rate of MRD clearance
Assess impact of SEA-BCMA in combination with SOC therapies on health-related quality of life (HRQoL) from the subject's perspective.	Descriptive outcomes of qualitative interviews

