5 STATISTICAL CONSIDERATIONS

5.1 General Principles

This is a phase 1 dose-escalation study. All analyses will be descriptive; however, confidence intervals may be presented to describe precision of estimates.

Descriptive statistics (mean, median, standard deviation, minimum, and maximum) will be used to summarize continuous variables. Frequencies and percentages will be used to summarize categorical variables. The two-sided 95% exact confidence interval using Clopper-Pearson methodology ([Collett 1991](#)) will be calculated for the response rates where applicable (e.g., ORR).

The median survival time will be estimated using the Kaplan-Meier method; the associated 95% confidence interval (CI) will be calculated based on the complementary log-log transformation ([Collett 1994](#)).

Unless otherwise specified, data are to be summarized by dose level and overall. DLT summarization will only include patients in the dose escalation part of the study, and will be done by dose level. For all other analyses, patients treated in the dose escalation part of the study may be pooled together with patients treated at the same dose level in the expansion cohorts.

Any analysis not described in this plan will be considered exploratory, and will be documented in the clinical study report (CSR) as a post hoc analysis or a change to the planned analysis.

To comply with regulatory electronic submission guidelines, listings of all clinical data will be submitted as electronic data sets. To facilitate data review for the study report, only pertinent data listings will be created and attached to the appendix of the CSR. All statistical output will be produced using SAS[®], version 9.3 or more recent. Other statistical software, if used, will be described in the clinical study report.

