6.6 Safety Analyses

The All Treated Patients analysis set will be used to summarize all safety endpoints, by dose level and total.

Adverse events will be coded using Medical Dictionary for Regulatory Activities (MedDRA, Version 20.1 or higher).

Laboratory values and adverse events will be graded according to the National Cancer Institute Common Terminology Criteria for Adverse Events (NCI CTCAE version 4.03).

Concomitant medications will be coded using WHO Drug (version: June 2017 or more recent).

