6.6.1 Adverse Events

Adverse events will be summarized by MedDRA preferred term in descending frequency of occurrence unless otherwise specified. For incidence reporting, if a patient reports more than one AE that was coded to the same system organ class or preferred term, the patient will be counted only once for that specific system organ class or preferred term.

A treatment-emergent AE is defined as a newly occurring or worsening AE after the first dose of SEA-BCMA. An overall summary of AEs will be provided by dose level and total. Summaries of AEs will also be provided by dose level and total for the following, by preferred term, if not specified otherwise:

- All treatment-emergent AEs
- AEs related to SEA-BCMA
- Serious Adverse Events (SAEs)
- SAEs related to SEA-BCMA
- AEs leading to dose elimination of SEA-BCMA
- AEs leading to dose delay of SEA-BCMA
- AEs leading to dose interruption of SEA-BCMA
- AEs leading to dose reduction of SEA-BCMA
- AEs leading to treatment discontinuation
- AEs leading to death
- Infusion related reactions by preferred term
- Adverse Events considered as DLT
- Treatment-emergent AEs by system organ class, preferred term and maximum severity
- Grade 3–5 treatment-emergent AEs
- Treatment-emergent AEs by system organ class and preferred term

All adverse events, adverse events leading to treatment discontinuation, and adverse events leading to death will be listed.

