8.2 Changes from the Original SAP

Efficacy-Evaluable Analysis Set, PK Analysis set were not used in the final CSR analysis.

The following Subgroups will not be explored.

- Cytogenetic risk group (high, intermediate, normal)
- Refractory to prior therapies (refractory to IMiD and PI vs not; refractory to IMiD and PI and anti-CD38 antibody vs not)
- Number of prior therapies (<5 vs \geq 5)
- Baseline beta-2 microglobulin (<3.5 vs \geq 3.5)
- ISS stage at initial diagnosis (1, 2, 3)
- MRD-negative CR rate and its exact two-sided 95% confidence interval will also be presented.

MRD negative CR, and duration of CR is not summarized.

Exploratory analyses which will be covered by Biomarker Analysis Plan are removed.

IRR by cycle analysis is removed.

ECG summary analysis is removed.

REFERENCES

Clopper CJ and Pearson ES (1934). The use of confidence or fiducial limits illustrated in the case of the binomial. *Biometrika* 26: 404-413.

Collett D (1991). Statistical inference for binary data. *Modelling Binary Data*. London, Chapman and Hall: 23-26.

Collett D (1994). Interval-censored survival data. *Modelling survival data in medical research*. Boca Raton, Fla., Chapman & Hall/CRC: 237-251.

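### Infusion-related reactions are planned only by dose level and total, so the total column does, and the 1600 mg column can, mix regimens that differ in premedication, schedule and combination partner

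*SAP*

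**What the plan says.** SAP 6.6 sets the layout for safety: "The All Treated Patients analysis set will be used to summarize all safety endpoints, by dose level and total". SAP 6.6.1 repeats that layout for the adverse event summaries and lists the only dedicated IRR table, "Infusion related reactions by preferred term". SAP 5.1 restricts DLT summaries to escalation patients. For everything else, it says that escalation patients "may be pooled together with patients treated at the same dose level in the expansion cohorts". SAP section 3 and the protocol synopsis use the term expansion cohort for Part B, for both Part C cohorts and for Part D, so the permission reaches across parts. No safety table is specified by part, schedule, premedication or combination partner. By contrast, SAP 6.5.1.3 does ask for results per expansion cohort for duration of response.

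The regimens at one dose differ. Protocol 5.5 states: "In Parts B through D, routine premedication for infusion reactions must be administered prior to SEA-BCMA infusion". Part A has no such standing rule; premedication there depends on the SMC (protocol 3.1.9.1) or on the Grade 3 IRR trigger in protocol 3.1.5. Parts C and D also give dexamethasone 1 to 3 hours before SEA-BCMA (protocol 5.3.3). Protocol 5.3.1 notes, for other approved antibodies, that "dexamethasone is administered as premedication for monoclonal antibodies".

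**The concern.** Adverse event incidence is a primary endpoint. Safety of monotherapy and safety of combination therapy are separate primary objectives (SAP section 2, Table 1). A 1600 mg column that pools Parts A to D answers neither. The endpoint for the recommended single-agent dose and schedule is "cumulative safety and activity by dose level and schedule", yet a pooled column would put q2wk and weekly-induction monotherapy together.

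The 100, 200 and 400 mg levels exist only in Part A escalation, while 1600 mg is used in every part. A reader who looks across the dose columns would therefore compare mostly unpremedicated q2wk monotherapy with a mixture. IRRs could seem to fall with dose when dose has no effect, or a real rise could be hidden.

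**Working it through.** **Plan's own figure.** SAP 5.3 gives about 131 patients: 45 + 20 + 60 + 6 = 131. This reproduces.

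**Who can sit in the 1600 mg column, at planned ceilings**

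| Group | Number | Schedule | Required premedication | Partner | Source |
|---|---|---|---|---|---|
| Part A escalation | 6 (DLT-evaluable) | q2wk | no | none | Protocol 3.2.1.1 |
| Part A expansion | 20 | q2wk | no | none | Protocol 3.1.1.2, 3.2.1.1 |
| Part B | 20 | weekly, then q2wk | yes | none | Protocol 3.1.2 |
| Part C Cohort 1 | 20 | q2wk | yes | dexamethasone | Protocol 3.1.3.2 |
| Part C Cohort 2, if escalated | 20 | weekly, then q2wk | yes | dexamethasone | Protocol 3.1.3.2 |
| Part D | 6 | q2wk | yes | pomalidomide, dexamethasone | Protocol 3.1.3.3 |

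Part A: 6 + 20 = 26. Parts B-D: 20 + 20 + 20 + 6 = 66. Total 92. Shares: 26/92 = 0.283 and 66/92 = 0.717. The other 131 - 92 = 39 are Part A below 1600 mg (25 - 6 = 19) and Part C Cohort 2 at 800 mg (20).

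**Formula.** Let p0 be the IRR rate without premedication and p1 the rate with it, the same at every dose. Assume for now that premedication follows part and that schedule and partner have no effect.
- 1600 mg column = (26 × p0 + 66 × p1) / 92
- False gap against the 100-400 mg columns = 0.717 × (p0 - p1)

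**Results.** The documents give no IRR rates, so these are assumptions.
- p0 = p1 = 30%: the column shows 30%, with no distortion.
- p0 = 30%, p1 = 15%: (7.8 + 9.9)/92 = 19.2%, against 30% at 100-400 mg, a false gap of 10.8 points.
- p0 = 40%, p1 = 20%: (10.4 + 13.2)/92 = 25.7%, against 40%.
- Masking: suppose the unpremedicated rate truly rises from 20% at 100-400 mg to 40% at 1600 mg, and Parts B-D have 20%. The column shows (10.4 + 13.2)/92 = 25.7%, so a 20-point rise appears as 5.7 points.

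**Sensitivity to enrolment** (30%/15%). If Part B de-escalates after 6 patients and Part C Cohort 2 does not escalate, the column holds 26 + 6 + 20 + 6 = 58 and Part A's share is 26/58 = 45%. The gap is then (32/58) × 15 = 8.3 points. Part A's share therefore lies between 28% and 45%.

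**Other columns** (30%/15%).
- Total: (45 × 30 + 86 × 15)/131 = 20.2%.
- 800 mg, with 20 from Part C Cohort 2 and an assumed 2, 3 or 6 from Part A: 16.4%, 17.0% or 18.5%.

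**Would a split by schedule be enough?** No. The 1600 mg q2wk column would still hold 26 Part A patients and 20 + 6 = 26 from Part C Cohort 1 and Part D, an even mixture.

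**The case against.** The strongest reply is that the SAP permits pooling but does not require it. Dose level is not defined as milligrams across parts, and the protocol uses the term for levels within a part. Protocol 9.3.9.2 speaks of adverse events by treatment group, and SAP Table 1 mentions schedule. Programmers could therefore split the columns without breaching the SAP. This stands for the 1600 mg column, where mixing is possible but not certain. It does not help the total column, which mixes in any case. Neither the treatment-group nor the schedule wording is carried into SAP 6.6.1.

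Premedication also does not follow part exactly. The SMC could require it in Part A. Protocol 5.5 allows exceptions in Parts B-D, and protocol 5.7.1 lets the SMC modify or omit it. The document history adds Parts B and C in Amendment 3 but records the required regimen only in Amendment 6, about 13 months later. So the 66 of 92 is the share under a standing requirement, not a count of patients who were premedicated. This also stands, and it is why a split by part alone is not enough.

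Finally, all analyses are descriptive, DLTs are kept separate, 1600 mg q2wk had already been chosen, the SMC reviews run-in data by cohort, and listings would let someone rebuild the split. These points limit the consequence. They do not correct the planned table.

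Three stronger readings are tempting. A reader might take the Amendment 3 rationale, "as IRRs have not yet been correlated with dose, and all IRRs that occurred during Cycle 1 Day 1 were successfully prevented by premedication", as evidence that premedication and not dose drives IRRs. It is an interim remark made while the study was under way, and the absence of a reaction at the next infusion has no unpremedicated comparator. A reader might also assume that premedication in Part A would only shrink the problem. If the 20 expansion patients at 1600 mg were premedicated, the premedicated share would rise from 66/92 to 86/92 = 0.935, and at 30%/15% the false gap would widen from 10.8 to 14.0 points. Lastly, "IRR by cycle analysis is removed" might be cited as support, but that is a declared change about timing and does not bear on mixing parts.

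**Conclusion.** The point holds as a defect of layout. As written, the total column mixes regimens and the 1600 mg column may. Where they are mixed, the incidence belongs to no regimen, and differences between doses cannot be separated from premedication, schedule and combination partner.

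The size cannot be stated from the documents. The 30% against 19.2% example rests on assumed rates, full enrolment, premedication that follows part, and no effect of schedule or partner. With the smaller 1600 mg column the gap is about 8 points; with no premedication effect it is zero. A reader might infer that the table will show IRRs falling with dose. The documents support only that it could. The harm is to interpretation of a primary safety endpoint; no error rate or dose-escalation decision is affected.

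**What to change.** In SAP 6.6.1, present IRRs by part and cohort: Part A by dose; Part B; Part C Cohort 1; Part C Cohort 2 at 800 mg and at 1600 mg; Part D. State that Part A is not pooled with Parts B-D for IRRs. Compare doses only within Part A, split by whether premedication was given before the first infusion.

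The cost is SAP wording and different table columns. Part, cohort, dose and adverse event terms are already recorded, as are concomitant medications from Day 1 predose (protocol 5.6, 7.7.3.2). The columns become smaller and the intervals wider: for example 10/26 has an exact 95% interval of 20% to 59%, and 4/20 has 6% to 44%. For a descriptive table this is acceptable, since each figure then refers to a regimen that patients actually received.

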6.6.1.1 Adverse Events of Special Importance

Adverse events of infusion related reactions(IRRs) and associated symptoms may be considered AEs of special importance.

6.6.2 Dose-Limiting Toxicity

The observed number and proportion of patients experiencing a DLT will be reported for the dose escalation part of the study. At each dose level, model-based estimates of the probability of DLT will be presented along with the corresponding 95% credible intervals.

6.6.3 Clinical Laboratory Parameters

Clinical laboratory data will be summarized for selected lab tests, by dose level and scheduled visit. Summary statistics may be tabulated where appropriate. The worst post baseline grade will be presented by dose level and total for each lab test.

Laboratory results and NCI CTCAE grades for hematology, and serum chemistry will be presented in data listings. All laboratory data through the end of treatment visit will be presented in standardized units.

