2. OBJECTIVES

This study will evaluate the safety and antitumor activity of SEA-BCMA as monotherapy and in combination in subjects with RRMM. Specific objectives and corresponding endpoints are detailed in [Table 1](#).

Table 1: Objectives and corresponding endpoints

Primary Objectives	Corresponding Primary Endpoint
Evaluate the safety and tolerability of SEA-BCMA monotherapy in subjects with relapsed or refractory multiple myeloma (RRMM) Identify the maximum tolerated dose (MTD) and/or optimal dose and schedule of SEA-BCMA monotherapy, and in combination with dexamethasone, in subjects with RRMM	Type, incidence, severity, seriousness, and relatedness of adverse events (AEs) Type, incidence, and severity of laboratory abnormalities Incidence of dose-limiting toxicities (DLTs)
Evaluate the safety and tolerability of SEA-BCMA in combination with SOC therapies in subjects with RRMM	
Secondary Objectives	Corresponding Secondary Endpoints
Identify a recommended single-agent dose and schedule of SEA-BCMA Assess the pharmacokinetics (PKs) of SEA-BCMA Assess the immunogenicity of SEA-BCMA Assess the antitumor activity of SEA-BCMA	Incidence of DLTs, cumulative safety and activity by dose level and schedule Maximum serum concentration and area under the serum concentration-time curve Incidence of SEA-BCMA antitherapeutic antibodies (ATA) Best response per the International Myeloma Working Group (IMWG) uniform response criteria (Kumar 2016) Objective response rate (ORR) Duration of objective response (OR) and complete response (CR) Progression-free survival (PFS) Overall survival (OS)
Exploratory Objectives	Corresponding Exploratory Endpoints
Assess incidence and level of BCMA expression in RRMM and relationship to clinical response to SEA-BCMA Assess the pharmacodynamic effects and biomarkers of response, toxicity, and resistance to SEA-BCMA Assess minimal residual disease (MRD) in subjects with very good partial response (VGPR) or better Assess impact of SEA-BCMA in combination with SOC therapies on health-related quality of life (HRQoL) from the subject's perspective.	Characterization of BCMA expression on malignant plasma cells Exploratory biomarkers of SEA-BCMA mediated pharmacodynamic effects Rate of MRD clearance Descriptive outcomes of qualitative interviews Maximum serum concentration and area under the serum concentration-time curve

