7. The following baseline laboratory data (hematologic criteria must be met in the absence of growth factor or platelet transfusion support):
 - a. Estimated glomerular filtration rate (eGFR) ≥ 30 mL/min/1.73 m² per the Modification of Diet in Renal Disease (MDRD) equation ([Appendix I](#))
 - b. Absolute neutrophil count $\geq 1000/\mu\text{L}$
 - c. Platelet count $\geq 75,000/\mu\text{L}$
8. For Parts A, B, and C: Subjects of childbearing potential, as defined in Section [4.3](#), under the following conditions:
 - a. Must have a negative serum or urine pregnancy test (minimum sensitivity 25 mIU/mL or equivalent units of beta human chorionic gonadotropin [β -hCG]) result within 7 days prior to the first dose of SEA-BCMA. Subjects with false positive results and documented verification that the subject is not pregnant are eligible for participation
 - b. Must agree not to try to become pregnant during the study and for at least 6 months after the final dose of any study drug administration
 - c. Must agree not to breastfeed or donate ova, starting at time of informed consent and continuing through 6 months after the final dose of any study drug
 - d. If sexually active in a way that could lead to pregnancy, must consistently use 2 highly effective methods of birth control (as defined in [Appendix E](#)) starting at time of informed consent and continuing throughout the study and for at least 6 months after the final dose of any study drug
9. For Parts A, B, and C: Subjects who can father children, under the following conditions:
 - a. Must agree not to donate sperm starting at time of informed consent and continuing throughout the study period and for at least 6 months after the final dose of any study drug
 - b. If sexually active with a person of childbearing potential in a way that could lead to pregnancy, must consistently use 2 highly effective methods of birth control (as defined in [Appendix E](#)) starting at time of informed consent and continuing throughout the study and for at least 6 months after the final dose of any study drug
 - c. If sexually active with a person who is pregnant or breastfeeding, must consistently use 1 of 2 contraception options (as defined in [Appendix E](#)) starting at time of informed consent and continuing throughout the study and for at least 6 months after the final dose of study any drug.

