9.3.9.5. Clinical Laboratory Results

Laboratory values (eg, chemistry, hematology, urinalysis, and pulmonary function tests) may be presented graphically by visit. Summary statistics may be tabulated as appropriate by scheduled visit. Laboratory values will be listed with grade per NCI-CTCAE v. 4.03 and flagged when values are outside the normal reference range.

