6.6.6 ECOG Performance Status

Shifts from baseline to the best and worst post-baseline score will be tabulated.

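### SAP 6.6.3 tabulates laboratory grades only as the worst grade after baseline, so abnormalities present at entry that persist are counted in the on-treatment incidence

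*SAP*

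**What the plan says.** Protocol Section 2 (Table 1) and the matching SAP table list "Type, incidence, and severity of laboratory abnormalities" among the primary endpoints.

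SAP 6.6.3 plans three outputs:

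- a graded table: "The worst post baseline grade will be presented by dose level and total for each lab test";
- by-visit summaries: "Clinical laboratory data will be summarized for selected lab tests, by dose level and scheduled visit";
- listings: "Laboratory results and NCI CTCAE grades for hematology, and serum chemistry will be presented in data listings".

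Protocol 9.3.9.5 adds possible plots and summary statistics by visit, and a listing: "Laboratory values will be listed with grade per NCI-CTCAE v. 4.03 and flagged when values are outside the normal reference range". Neither section relates a subject's post-baseline grade to the grade at baseline.

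Elsewhere the SAP does use baseline. Section 6.6.6 says of ECOG status: "Shifts from baseline to the best and worst post-baseline score will be tabulated". Section 6.6.1 counts an AE as treatment-emergent only if it is new or has worsened since the first dose.

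**The concern.** Subjects may enter with abnormal laboratory values. Protocol 4.1 (criterion 7) accepts neutrophils from 1000/µL, platelets from 75,000/µL and eGFR from 30 mL/min/1.73 m²; of the blood counts it asks only that "hematologic criteria must be met in the absence of growth factor or platelet transfusion support". Protocol 4.2 (criterion 16) excludes ALT or AST only above 3×ULN, and bilirubin only above 1.5×ULN (3×ULN with Gilbert's disease). Haemoglobin has no entry limit, although Protocol 1.1 describes anaemia as a consequence of the disease.

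A subject who enters with anaemia of a given grade and stays there appears in the worst-grade table at that grade, just like a subject who developed it on SEA-BCMA. The table therefore mixes disease at entry with change on treatment. Eligibility also differs between parts (Protocol 4.1, criterion 2), and SAP 5.1 allows escalation and expansion subjects at the same dose to be pooled. Columns could differ partly because of who was enrolled.

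**Working it through.** The plan gives no figure on this point to reproduce. The check compares the sections and then illustrates the mechanism.

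**1. Does any planned output remove the baseline contribution?**

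- *Worst-grade table (SAP 6.6.3):* takes the maximum grade after baseline and uses no baseline grade. Chemistry and blood counts are drawn on Days 1, 8, 15 and 22 (Protocol Section 6), so a persistent abnormality will reach at least its entry grade.
- *By-visit summaries (SAP 6.6.3):* cover selected tests and may include the baseline visit, but do not give each subject's change in grade.
- *Listings (SAP 6.6.3, Protocol 9.3.9.5):* carry grades, so baseline can be compared by hand, but nothing is tabulated.
- *AE tables (SAP 6.6.1):* account for baseline. However, Protocol 7.7.1.1 generally keeps a laboratory value off the AE form unless it causes symptoms, needs intervention, leads to an SAE, or interrupts or ends treatment or participation. Most asymptomatic changes are therefore seen only in the laboratory outputs.

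No planned table separates new or worsened grades from persistent ones. SAP 5.5 defines baseline as the last non-missing value before first dose, so a baseline grade can be derived.

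**2. Which grades are affected?**

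For tests with an entry limit, a subject can carry in only what the limit allows, and Protocol Section 4 requires eligibility to hold within 1 day of dosing on Cycle 1 Day 1. The CTCAE cut-offs are not in the documents. I take it as an assumption that the listed limits correspond to grades below 3. For tests without a limit, such as haemoglobin, any grade could be carried in.

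**3. Size, by illustration only.**

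One persistent baseline case in N subjects adds 1/N to the incidence at its grade. For N = 20 this is 1/20 = 5 percentage points.

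More generally, let a share b have the abnormality at entry and remain at that grade, and let a share q of the others develop it:

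- reported in the worst-grade table: b + (1 − b)q
- new on treatment: (1 − b)q

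With N = 20 and q = 10% (b and q both assumed, abnormality of any grade):

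| b | Reported | New |
|---|---|---|
| 10% | 20 × (0.10 + 0.90 × 0.10) = 3.8 | 20 × 0.90 × 0.10 = 1.8 |
| 25% | 20 × (0.25 + 0.75 × 0.10) = 6.5 | 20 × 0.75 × 0.10 = 1.5 |
| 50% | 20 × (0.50 + 0.50 × 0.10) = 11.0 | 20 × 0.50 × 0.10 = 1.0 |

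With no drug effect (q = 0), the binomial chance that at least 5 of 20 subjects appear abnormal is 4.3%, 58.5% and 99.4% for b = 10%, 25% and 50%.

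**The case against.** The strongest reply is that the table drives no decision. Part A escalation uses DLT counts in the mTPI table (Protocol 3.1.1.1), and the run-ins in Parts B, C and D use DLT counts (3.1.2, 3.1.3). The DLT definition (3.1.5) is separate from this table. It judges asymptomatic laboratory abnormalities against Grade 1 or the baseline grade, and counts Grade 4 anaemia only if unrelated to the underlying disease. Escalation was complete, with no DLT in 6 subjects at 1600 mg (3.2.1.1). All analyses are descriptive, and in cohorts this small a reader can find baseline grades in the listings.

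All of this stands, and it limits the point. A reader might infer that the defect undermines dose selection or the comparison of schedules. The documents do not support that: no escalation or run-in rule takes the worst-grade table as input. The objective of recommending a single-agent dose and schedule does draw on cumulative safety, so the table may inform judgement, but not through a stated rule.

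A reader might also infer that Grade 3 or higher rates are inflated by a known amount across cytopenias and organ function. That does not follow either. None of the listed entry limits is shown to reach Grade 3, and the documents give no count of subjects entering at that grade. For Grade 3 or higher the argument rests on tests without an entry limit.

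The reply does not show that the planned summary of a primary endpoint is adequate. Recovering baseline by hand from listings does not replace a tabulation.

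**Conclusion.** The point holds for the descriptive laboratory safety summary. As written, SAP 6.6.3 counts persistent entry abnormalities as on-treatment incidence: lower-grade cytopenias and the renal or hepatic values that entry allows, and any grade for tests without an entry limit, such as haemoglobin. DLT counts, mTPI decisions and run-in decisions are unaffected.

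The size is unknown because no baseline distribution is given. The 5 points per case in a cohort of 20 is arithmetic; how many such cases there would be is not known. The other illustrations rest on assumed prevalences and on baseline abnormalities staying at their entry grade. The change is worth making because this is a primary endpoint, the AE tables do not cover most asymptomatic values, and the SAP already uses baseline for ECOG and AEs.

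**What to change.** In SAP 6.6.3:

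- add, for each graded test, a table of shift from baseline grade to worst post-baseline grade, by dose level and cohort;
- report treatment-emergent incidence, defined as a post-baseline grade higher than the baseline grade, in the same layout;
- keep the current worst-grade table as supportive.

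The baseline definition in SAP 5.5 can be used unchanged, and no new data are needed. The cost is one additional standard table. Specifying it in the SAP also matters because SAP 5.1 treats any analysis outside the plan as exploratory. The shift table will not separate drug effect from worsening disease, which uncontrolled cohorts cannot do, but it will remove what was already present at entry.
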